6.3.2. Secondary efficacy analysis

All secondary efficacy analyses will be based on the Safety Set. The analyses performed at eye level will focus on the study eye only.

6.3.2.1. *Optical coherence tomography angiography (OCTA) parameters*

Definition

Optical Coherence Tomography Angiography (OCTA) is a non-invasive imaging modality that provides cross-sectional, three-dimensional and high-resolution imaging of the retinal and choroidal vasculature with micrometer-scale depth resolution. It does not require any dye injection and allows the retinal and choroid vessels to be viewed dynamically.

Optical Coherence Tomography Angiography (OCTA) images will be obtained and assessed in the study eye at every study visit and in the fellow eye at Screening and Week 48. The OCTA images will be evaluated by the CRC considering only images on study eye during the study (except screening visit). The OCTA images on fellow eye and on study eye at screening will be only stored but not grading.

On OCTA images grading by CRC, the following qualitative parameter will be measured:

- Branching vessels: evaluate the width of vessel respect to previous read. The presence of tiny vessels branching from bigger vessels is indicative an active CNV lesion. The possible values will be 'increased from prior' (i.e., possible active CNV lesion), 'decreased from prior', 'stable', 'N/A (baseline)' (of note, this will be expected for baseline since there is not a previous image to be compare), 'UNG/P', 'UNG/Q'.
- Peripheral Anastomotic Arcades: possible values will be 'No', 'Yes', 'UNG/P', 'UNG/Q' and in case of presence (i.e., 'Yes') of peripheral anastomotic arcades at the vessel termini is indicative of an active CNV lesion.
- Vascular Loops: possible values will be 'No', 'Yes', 'UNG/P', 'UNG/Q'. The presence of vascular loop (i.e., anatomical anomalies) is indicative of an active CNV lesion.
- Dark Halo: possible values will be 'No', 'Yes', 'UNG/P', 'UNG/Q'. The presence of dark halo that are hypointense area considered as a region of choriocapillaris alteration, corresponding to local flow impairment and is indicative of an active CNV lesion.

| | |
|--|----------------------------------|
| | Statistical Analysis Plan |
| | Sponsor: Novartis |
| | Protocol: CRTH258AIT04 |

In addition, the presence of CNV lesion is evaluated and described according to the following possible values: 'No', 'Yes', 'UNG/P', 'UNG/Q'. If CNV lesion is present, a description of its involvement of the foveal center will be provided always based on the values 'No', 'Yes', 'UNG/P', 'UNG/Q' together with details about the following quantitative parameters:

- CNV flow size: visualized by calculating the decorrelation of signal amplitude from consecutive B-scans, thus creating a contrast between static and non-static tissue, through an appropriate algorithm. To quantify the blood flow within the CNV, the CNV area and flow index were calculated from the 2D maximum projection outer retina CNV angiogram. The parameters related to CNV flow size are Total CNV lesion area (mm²) and Greatest linear diameter of lesion (mm).
- Vessel density of the lesion: calculated as a ratio of the area occupied by vessels to the total area of the lesion that is reported as CNV vascular density (%).

Analysis methodology

Firstly, a description for the OCTA imagines' quality will be provided at each visit reporting the proportion of images with quality concerns present and a description of the issue detected that could be one or more of the following:

- NOT PER PROTOCOL/INCOMPLETE
- OFF-FOVEA
- MOTION ARTIFACT
- PROJECTION ARTIFACT
- SEGMENTATION ERROR
- DEGRADED IMAGE
- OTHER

Similarly, the proportion of imagines with quality concerns that prevent any grading is provided together with the issue(s) detected (one or more than one among the list previously described).

All qualitative and quantitative parameters described above will be described overall at each visit in terms of absolute and relative frequencies or as continuous variable, respectively.

For quantitative variables (i.e., Total CNV lesion area (mm²) and Greatest linear diameter of lesion (mm) and CNV vascular density (%)), absolute changes from baseline will be computed and summarized at each visit. A paired t-test or Wilcoxon

| | |
|--|----------------------------------|
| | Statistical Analysis Plan |
| | Sponsor: Novartis |
| | Protocol: CRTH258AIT04 |

signed rank test, based on data distribution, will be used to test the difference at each time point vs Baseline.

For all qualitative variables except Branching vessels (excluded since this variable provided as result the comparison to the previous read and not a status at each visit), shift table of each post-baseline visit vs Baseline will be provided. A McNemar test Test will be used to test the difference at each post-baseline visit vs baseline. Of note, shift tables will be provided considered only patients for whom baseline and post-baseline value are both available (i.e., parameter considered equal to 'No' or 'Yes').

Data handling rules

An observed approach will be considered for all the analysis.

Sensitivity of secondary analysis

Not applicable.

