12.5 Analysis of secondary endpoints

12.5.1 Efficacy and/or Pharmacodynamic endpoint(s)

All secondary efficacy analyses will be based on the FAS. The analyses performed at eye level will focus on the study eye only.

The secondary efficacy objective and endpoints of this study are as follows:

To evaluate the effect of brolucizumab on the evolution of qualitative and quantitative OCTA parameters of wAMD from Baseline to Week 48

Summary statistics of each parameter assessed by OCTA, of which the main quantitative parameters are CNV flow size and vessel density, and the main qualitative ones are branching vessels, peripheral anastomotic arcades, vascular loops and dark halo, from Baseline up to Week 48 will be provided, including changes vs Baseline. Paired t-test or Wilcoxon signed rank test, based on data distribution, will be used to test the difference at each time point vs Baseline for continuous parameters. In case of a dichotomous parameter, a McNemar test will be used.

To evaluate the effect of brolucizumab on the evolution of qualitative and quantitative SD-OCT parameters of wAMD from Baseline to Week 48

Summary statistics of each parameter assessed by SD-OCT, of which the main quantitative parameters are CRT and PED volume, and the main qualitative ones are IRF, SRF, sub-RPE fluid, status of ELM, SHRM and outer retinal tubulation, from Baseline up to Week 48 will be provided, including changes vs Baseline.

Paired t-test or Wilcoxon signed rank test, based on data distribution, will be used to test the difference at each time point vs Baseline for continuous parameters. In case of a dichotomous parameter, a McNemar test will be used.

To evaluate the effect of brolucizumab on the evolution of functional parameters of wAMD from Baseline to Week 48

Summary statistics of BCVA from Baseline at each visit up to Week 48 as well as changes vs Baseline will be provided. Paired t-test or signed rank test, based on data distribution, will be used to test the difference at each time point vs Baseline.

Frequency of patients with an improvement of at least 5/10/15 letters or worsening will be also provided.

To evaluate the effect of brolucizumab on sustained dryness from Baseline to Week 48

- Time to reach sustained dryness of the study eye, as defined by the absence of IRF and SRF for at least 2/3 consecutive visits, will be descriptively summarized. Survival Kaplan-Meier curve will also be provided including summary estimates.

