For what concern the LOCF approach reported in the study protocol, this approach will be maintained for the predictors to be included in the analysis of the primary endpoint since the focus is on the first visits (from baseline to Week 16) and all enrolled patients should perform these visits independently of treatment regimen that will be followed by each patient. For the secondary endpoints, LOCF approach will not be applied because after Week 16 each patient will have different scheduled of visits based on treatment regimen. The LOCF approach can be considered only until Week 16 but (1) for OCTA the number of missing data will lead to most data imputed than the one observed, (2) for SD-OCT the approach is applied in the analysis of primary endpoint, (3) for BCVA the LOCF approach will be provided until Week 16, (4) for HAD and EQ-5D-5L questionnaires the LOCF approach will not be applied since only two assessments of these questionnaires are planned in the study.

As performed for interim analysis, all analysis will be conducted on Safety population since during the interim analysis, in which all enrolled patients were considered (see section 6.6 for further details), the FAS and Safety populations include the same set of patients since per definitions of the study protocol, the FAS considered all enrolled patients who completed the baseline visit and all of them are treated and consequently all of them belong to Safety population.

The evaluation of prevalence of anxiety and depression will be performed only based on HAD questionnaire and not based in terms of treatment that patients could have received for anxiety/depression.

The following additional analysis will be included:

- SD-OCT parameters at baseline and type of predominant lesion will be also analyzed according to BCVA groups and CST groups based on changes at Week 12 in patients who performed Week 16 and were still on treatment at this timepoint.
- A graphical representation of BCVA ETDRS score and CST by means of spaghetti plot will be provided.
- Analyses on CST and BCVA will be also performed on patients with BCVA ETDRS score lower than 69 letters at baseline.

| | |
|--|----------------------------------|
| | Statistical Analysis Plan |
| | Sponsor: Novartis |
| | Protocol: CRTH258AIT04 |

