4.4.2. Handling of Missing Data/Imputation/Censoring Rules

For the primary endpoint, patients who prematurely discontinued the study should be considered as not being q12w fluid-free at Week 48.

The following missing Imputation Rules should be considered for the secondary endpoints:

- The last observation carry-forward (LOCF) method will be used to handle Missing data.
- As observed approach will be also considered.

Censoring rules will be applied for the time to sustained dryness and described in the section 6.3.2.4 of the present document.

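### OCTA lesion area and diameter exist only while a CNV lesion is graded present, so an eye whose measured lesion is later graded absent leaves the paired size-change analysis because of its outcome

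*SAP*

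**What the plan says.** In SAP 6.3.2.1 the reading center grades CNV lesion presence on OCTA as 'No', 'Yes', UNG/P or UNG/Q. Size is conditional on that grade: "If CNV lesion is present, a description of its involvement of the foveal center will be provided always based on the values", and the sentence continues "together with details about the following quantitative parameters". The list that follows holds Total CNV lesion area (mm²) and Greatest linear diameter (mm), both under CNV flow size, and CNV vascular density (%).

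For these variables "absolute changes from baseline will be computed and summarized at each visit", with a paired t-test or Wilcoxon signed rank test. This carries out Protocol 12.5.1, where such a test "will be used to test the difference at each time point vs Baseline for continuous parameters". The data handling rule in SAP 6.3.2.1 is "An observed approach will be considered for all the analysis", and sensitivity analysis is marked not applicable. Neither document assigns a value to area or diameter when the lesion is graded 'No'.

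Lesion presence is analysed in its own right. SAP section 2 lists it among the OCTA qualitative parameters. SAP 6.3.2.1 gives those parameters, apart from branching vessels, a shift table and a McNemar test against baseline at each later visit, using eyes graded 'Yes' or 'No' at both visits.

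**The concern.** Change in CNV flow size is part of secondary endpoint 1 (Protocol Table 2-1; SAP section 2). Going from a measured lesion to none detected is the largest reduction an eye can show, and 'No' is a grade that was obtained, not a failed reading. Inside the size-change tables, however, such an eye has no follow-up value and contributes no pair, just like an eye with an ungradable image. Whether an eye is included therefore depends on its outcome.

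At stake is what the tables mean. They would read as the change in lesion size in treated eyes but would describe only eyes whose lesion was still visible. The set of eyes can also differ from visit to visit, so a trend across visits mixes real change with changing membership.

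**Working it through.** The plan states no figure for this point, so there is none to reproduce. The check is a reading of the rules followed by algebra.

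**Reading the rules together**

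1. Size is provided only if the lesion is present (SAP 6.3.2.1).
2. Change from baseline needs a value at both visits, and only observed values are used (SAP 6.3.2.1).
3. No rule supplies a value for a graded absence. For the comparable FA sizes, SAP 6.2 gives an absent lesion a not-applicable code and summarises area only where it was measured. The one convention that is spelled out is therefore non-numeric.
4. LOCF does not change this. SAP 4.4.2 says of the secondary endpoints: "The last observation carry-forward (LOCF) method will be used to handle Missing data". SAP 1.1 drops LOCF for them and gives as its reason that "for OCTA the number of missing data will lead to most data imputed than the one observed". If LOCF were applied to a vanished lesion, it would carry a positive size forward.

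An eye that goes from 'Yes' to 'No' is therefore excluded from the paired size analysis.

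**Direction and size**

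None of these inputs is in the documents; all are assumed:

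- f: share of eyes with a measured baseline lesion that are graded 'No' at follow-up
- d: mean shrinkage in eyes whose lesion persists, with their mean baseline size set to 1
- r: mean baseline size of the lesions that vanish, in the same unit

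Formulas:

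- Present-only mean change = -d
- Mean change with absence counted as 0 = -[(1 - f)d + f·r]
- Shrinkage left out by the present-only analysis = f(r - d)

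Mean shrinkage is understated if r > d, unaffected if f = 0, and overstated if r < d.

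With d = 0.10, the present-only result is -0.10 at every f. With zeros it is:

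| f | r = 1.0 | r = 0.5 | r = 0.25 |
|---|---|---|---|
| 5% | -0.145 | -0.120 | -0.1075 |
| 10% | -0.190 | -0.140 | -0.115 |
| 20% | -0.280 | -0.180 | -0.130 |

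Example: f = 10%, r = 0.5 gives -(0.9 × 0.10 + 0.1 × 0.5) = -0.140.

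Reversal: d = 0.30, r = 0.25, f = 10% gives -(0.9 × 0.30 + 0.1 × 0.25) = -0.295, against -0.30 present-only.

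**Simulation, also on assumed inputs**

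Baseline area was lognormal (log-mean 0, log-SD 0.7), persisting eyes shrank by 10% on average, and smaller lesions were more likely to vanish. With 122 eyes, all gradable, the mean changes were:

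| f | Present-only | With zeros |
|---|---|---|
| 5% | -0.130 | -0.163 |
| 10% | -0.134 | -0.199 |
| 20% | -0.139 | -0.266 |

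Under these inputs, shrinkage is understated even though the vanishing lesions tend to be small.

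**The case against.** The strongest reply is that the SAP already reports disappearance. Read with SAP section 2, the shift table and McNemar test in 6.3.2.1 cover lesion presence. They count 'Yes'-to-'No' eyes at each visit and keep them apart from ungradable ones. Presence, plus size where present, is a legitimate two-part description. This stands as disclosure. It would be wrong to infer that the plan confuses absent with ungradable throughout, because that happens only inside the size tables. The shift table does not, however, alter the mean size change or its test.

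A reader might infer that shrinkage is bound to be understated. The documents do not support that. The direction reverses if the vanished lesions were smaller than the mean shrinkage of the rest. Eyes graded 'No' at baseline and 'Yes' later are also left out, and counting them from zero would pull the other way. For example, suppose persisting eyes change by -0.50 mm², 10% of eyes lose a 1.0 mm² lesion and 10% gain one. The mean is then 0.8(-0.50) - 0.10 + 0.10 = -0.40.

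A reader might also infer that a baseline 'No' should be scored 0. Inclusion criterion 3 (Protocol 5.1) requires active CNV at Screening, so a baseline OCTA 'No' is most plausibly non-detection. A zero there would create artificial growth once the lesion is imaged. Some post-baseline 'No' grades may be non-detection too.

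Finally, the reading center's grading charter is a separate document (Protocol 8.3.3) and might record 0 for an absent lesion. The SAP does not say so, and one sentence would settle it. The consequence is also limited: this is a secondary endpoint, and SAP 1.1 removes OCTA from the primary analysis.

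**Conclusion.** The gap in the derivation rules is clear from the SAP text. As written, the area and diameter changes and their tests describe eyes with a lesion measured at both visits, and eyes whose lesion is no longer seen are removed because of that result. Mean shrinkage is understated by f(r - d) when the vanished lesions' mean baseline size exceeds the persisting lesions' mean shrinkage.

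The size of the effect cannot be derived from the documents. It is nil if no lesion is graded absent, and the figures above rest wholly on assumed inputs, so no percentage bias should be attributed to this trial. The point covers area and diameter only, since vascular density is undefined without a lesion. It is a cheap improvement to a secondary analysis.

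**What to change.** In SAP 6.3.2.1:

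- For eyes with a measured lesion at baseline, set Total CNV lesion area and Greatest linear diameter to 0 at any post-baseline visit where CNV presence is graded 'No'. Keep UNG/P and UNG/Q as missing.
- Do not assign 0 at baseline.
- Leave CNV vascular density undefined when no lesion is present, and label its change table as covering eyes with a lesion at both visits.
- Report the present-only size analysis alongside, and read both with the planned presence shift table.

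The cost is one derivation rule, one table label and a second set of size results, with no new data. The small downside is that some post-baseline 'No' grades may be non-detection and not regression, which is why both results are shown.

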6.3.2.2. Spectral Domain Optical Coherence Tomography (SD-OCT)

Definition

OCT is a noninvasive imaging technique able to visualize structural changes of the neurosensory retina and the RPE through high-resolution cross-sectional (tomographic) images (B-scans). OCT systems based on the spectral domain technology, i.e. spectral-domain OCT (SD-OCT), allow dense scanning of the macula with an improved axial resolution and it allows to define the morphological features of the CNV complex, such as retinal thickening, and to detect early signs of CNV activity, such as intraretinal (IRF), subretinal (SRF) and under RPE (sub-RPE) fluid, intraretinal cystoid spaces and PED, as well as edema.

Spectral Domain Optical Coherence Tomography (SD-OCT) images will be obtained and assessed in the study eye at every study visit and in the fellow eye at Screening and at Week 48. Only SD-OCT machines can be used (i.e., no time-domain nor swept-source OCT). The SD-OCT images will be evaluated by the CRC considering only images on study eye during the study (except screening visit). The SD-OCT images on fellow eye and on study eye at screening will be only stored but not grading.

On SD-OCT images grading by CRC, the following qualitative parameter will be measured:

- Intraretinal fluid (IRF) that is the fluid that accumulates within the neurosensory retina due to the disruption of the external limiting membrane (ELM)-photoreceptor complex in the outer retina by the active CNV membrane. If IRF fluid was not absent (i.e., present or UNG/P or UNG/Q), also

| | |
|--|----------------------------------|
| | Statistical Analysis Plan |
| | Sponsor: Novartis |
| | Protocol: CRTH258AIT04 |

the following subcategories will be graded: (1) IRF in center 1 mm (i.e., fluid in the central 1 x 1-mm subfield) and (2) IRF at foveal center. Of note, the second one will be evaluated only in case IRF in 1 mm was not absent (i.e., present or UNG/P or UNG/Q). The possible values of these parameters will be 'No', 'Yes', 'UNG/P', 'UNG/Q'.

- Subretinal fluid (SRF) that is the fluid that commonly accumulates between the neurosensory retina and the RPE due to the profuse leakage from blood vessels of the CNV complex. If SRF fluid was not absent (i.e., present or UNG/P or UNG/Q), also the following subcategories will be graded: (1) SRF in center 1 mm (i.e., fluid in the central 1 x 1-mm subfield) and (2) SRF at foveal center. Of note, the second one will be evaluated only in case SRF in 1 mm was not absent (i.e., present or UNG/P or UNG/Q). The possible values of these parameters will be 'No', 'Yes', 'UNG/P', 'UNG/Q'.
- Sub-retinal pigment epithelium (sub-RPE) fluid that is the fluid that accumulates under the RPE, thus often leading to PEDs. If sub-RPE fluid was not absent (i.e., present or UNG/P or UNG/Q), also the subcategory sub-RPE in center 1 mm (i.e., considering the central 1 x 1-mm subfield) will be graded. The possible values of these parameters will be 'No', 'Yes', 'UNG/P', 'UNG/Q'.
- Subretinal Hyperreflective Material (SHRM) that is a poorly defined, medium-to-hyperreflective mass between the neurosensory layers and the RPE on SD-OCT, which is indicative of the neurovascular membrane, particularly in type II CNV lesions, and of disciform scar formation. If SHRM was not absent (i.e., present or UNG/P or UNG/Q), also the following subcategories will be graded: (1) SHRM in center 1 mm (i.e., considering the central 1 x 1-mm subfield) and (2) SHRM at foveal center. Of note, the second one will be evaluated only in case SHRM in 1 mm was not absent (i.e., present or UNG/P or UNG/Q). The possible values of these parameters will be 'No', 'Yes', 'UNG/P', 'UNG/Q'.
- Outer Retinal Tubulation (ORT) that are branching tubular structures located in the outer nuclear layer of the retina, which seems to be indicative of a rearrangement of degenerating photoreceptors in a variety of retinal diseases, including wAMD. If ORT was not absent (i.e., present or UNG/P or UNG/Q) also the subcategory ORT in center 1 mm (i.e., considering the central 1 x 1-mm subfield) will be graded. The possible values of these parameters will be 'No', 'Yes', 'UNG/P', 'UNG/Q'.
- Status of the ELM as an indicator of retinal integrity will be evaluated focusing on ELM integrity loss in center 1 mm (i.e., considering the central 1 x 1-mm subfield). The possible values will be 'No', 'Yes', 'UNG/P', 'UNG/Q'.
- In the study protocol, the Volume of Pigment-Epithelium Detachment (PEDs) defined as irregularly elevated lesions produced by the growth of the choroidal neovascular membrane and the accumulation of fluid or material in the sub-RPE space. On SD-OCT, PEDs appear as broad elevations of the RPE

| | |
|--|----------------------------------|
| | Statistical Analysis Plan |
| | Sponsor: Novartis |
| | Protocol: CRTH258AIT04 |

band relative to Bruch's membrane. The volume of PEDs is considered as a quantitative parameter evaluated by SD-OCT. However, it was not possible to measure this volume according to the CRC evaluation. Consequently, the following qualitative parameters will be provided: the presence of PED will be summarized considering the possible values (i.e., 'No', 'Yes', 'UNG/P', 'UNG/Q') and in case of PED presence, a description of the type of PED will be provided considering the predominant feature as fibrovascular only, predominantly fibrovascular, purely serous, predominantly serous, drusenoid PED, UNG/P, UNG/Q.

In addition, the following quantitative parameter will be measured:

- Central Retinal Thickness (CRT) measurement, as main quantitative morphological parameter of wAMD. The CRT evaluated in this study represents the average retinal thickness of the circular area within 1 mm diameter around the foveal center and it will be called as Center Subfield Thickness (CST) also known as foveal thickness and it will be measured in μm .

Analysis methodology

Firstly, a description for the SD-OCT images' quality will be provided at each visit reporting the proportion of images with quality concerns present and a description of the issue detected that could be one or more of the following:

- HIGH SPEED NOT HIGH RESOLUTION
- VOLUME SCAN ABSENT
- VOLUME SCAN INCOMPLETE
- RASTER/LINE SCAN ABSENT
- RASTER/LINE SCAN INCOMPLETE
- OFF-FOVEA
- MOTION ARTIFACT
- SCAN CLIPPING
- DEGRADED IMAGE
- POOR CONTRAST
- OTHER/ADDITIONAL DETAILS

Similarly, the proportion of images with quality concerns that prevent any grading is provided together with the issue(s) detected (one or more than one among the list previously described).

All qualitative and quantitative parameters described above will be described overall at each visit in terms of absolute and relative frequencies or as continuous variable, respectively.

| | |
|--|----------------------------------|
| | Statistical Analysis Plan |
| | Sponsor: Novartis |
| | Protocol: CRTH258AIT04 |

For quantitative variables (i.e., CST (μm)), absolute changes from baseline will be computed and summarized at each visit. A paired t-test or Wilcoxon signed rank test, based on data distribution, will be used to test the difference at each time point vs Baseline. A spaghetti plot of CST values at each timepoint will be provided by type of predominant CNV lesion (of note, 'UNG/Q' and 'UNG/P' evaluation of predominant CNV lesion will be considered in a unique category 'Ungradable').

CST will also be described considering only patients with BCVA ETDRS score lower than 69 letters at baseline in terms of descriptive statistics together with absolute changes from baseline and by means of spaghetti plot.

For the qualitative variables IRF, SRF, sub-RPE, SHRM, ORT and ELM integrity loss a shift table of each post-baseline visit vs Baseline will be provided. A McNemar test will be used to test the difference at each post-baseline visit vs baseline. Of note, shift tables will be provided considered only patients for whom baseline and post-baseline value are both available (i.e., parameter considered equal to 'No' or 'Yes') and moreover, the measurements of these qualitative parameters in center 1 mm and at foveal center will not be considering for shift tables.

Data handling rules

An observed approach will be considered for all the analysis.

Sensitivity of secondary analysis

Not applicable.

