6.7.2 Instruction for prescribing and taking study treatment

The study consists of a treatment period with brolucizumab from Baseline (Day 1) up to Week 48, as shown in [Figure 6-1](#).

Figure 6-1 Treatment regimen

As per Beovu® SmPC, the recommended dose of 6 mg brolucizumab (0.05 ml solution) is to be administered by intravitreal injection every 4 weeks (monthly) for the first 3 doses. Thereafter, the Investigator may individualize treatment intervals based on DA in the study eye as assessed by visual acuity and/or anatomical parameters (BCVA and/or IRF, SRF, sub-RPE fluid, hemorrhage, CRT and/or OCTA parameters and/or 3-field CFP). A first DA assessment is to be performed at Week 16, as recommended in Beovu® SmPC. In participants without DA, treatment every 12 weeks (q12w) should be considered. In patients with DA, treatment every 8 weeks (q8w) should be considered. DA will be first assessed at Week 16 and then at each subsequent scheduled q12w/q8w treatment visit. In participants on q12w regimen with DA at any of these visits, a q8w treatment regimen should be considered. In participants on q8w regimen without DA for two consecutive treatment visits in the opinion of the Investigator, the re-allocation to a q12w regimen should be considered.

Regardless of treatment administration, Baseline, Week 4, Week 8, Week 12, Week 16 and Week 48 visits are mandatory for all participants. The timepoints of the other treatment visits will depend on the treatment regimen of each participant (q12w/q8w). No monitoring visits are planned between the injection visits.

For all participants, the last potential study treatment will be at the Week 44 visit or at the Week 48 visit, according to the different treatment regimen implemented.

The different types of visits occurring through the study are summarized in [Table 6-3](#) with a description of when disease activity assessment and treatment take place.

Table 6-3 Disease activity assessment and treatment occurrence according to visit type

Type	Disease Activity Assessment	Treatment
Screening visit	No	No
Baseline (Day 1) visit	No	Yes
Week 4 and 8 visits	No	Yes
Week 12 visit	No	No

Type	Disease Activity Assessment	Treatment
Week 16 visit	Yes	Yes (if DA is present)
Treatment visits (every 8 or 12 weeks according to Investigator's decision)	Yes	Yes (every 8 or 12 weeks according to Investigator's decision)
Week 48 visit	Yes	Only if a treatment was planned at the visit, based on treatment regimen

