6.3.2.3. Best corrected visual acuity (BCVA)

Definition

The visual acuity is assessed by means of Best corrected visual acuity (BCVA). BCVA measurements will be taken in a sitting position using Early Treatment Diabetic Retinopathy Study (ETDRS) like visual acuity testing charts at an initial testing distance of 4 meters. The ETDRS chart has been established as the gold standard for objective VA measurement in clinical trials and consists of 14 rows of 5 letters each, for a total of 70 letters. A higher score represents better vision. BCVA will be assessed in the study eye at every study visit and in the fellow eye at Screening and Week 48. Only assessment on the study eye will be considered in the analysis.

Analysis methodology

BCVA ETDRS score in the study eye will be summarized at each visit by means of descriptive statistics for continuous variable together with absolute changes from baseline. A paired t-test or Wilcoxon signed rank test, based on data distribution, will

| | |
|--|----------------------------------|
| | Statistical Analysis Plan |
| | Sponsor: Novartis |
| | Protocol: CRTH258AIT04 |

be used to test the BCVA ETDRS score difference at each time point vs Baseline. A spaghetti plot of BCVA ETDRS score at each timepoint will be provided by type of predominant CNV lesion (of note, 'UNG/Q' and 'UNG/P' evaluation of predominant CNV lesion will be considered in a unique category 'Ungradable').

In addition, considering each post-baseline visit, the proportion of patients with improvement of at least 5, 10 and 15 letters in BCVA ETDRS score (i.e., absolute change greater or equal to 5, 10 and 15, respectively) will be provided. Similarly, the proportion of patients with worsening of at least 5, 10 and 15 letters in BCVA ETDRS score (i.e., absolute change less or equal to -5, -10 and -15, respectively) will be summarized.

The same analyses will be also repeated focusing on patients with BCVA ETDRS score at baseline lower than 69 letters.

Data handling rules

Firstly, an observed approach will be considered for all the analysis and the LOCF approach will be also applied but focusing only until Week 16 since after this timepoint the scheduled of visits will be different for each patient according to treatment regimen assigned.

Sensitivity of secondary analysis

Not applicable.

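### Pooled change-from-baseline results at Weeks 20, 24, 28, 36, 40 and 44 describe regimen-selected patients and cannot be read as one trajectory

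*SAP*

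**What the plan says.** SAP 6.3.2.2 sets the pattern for SD-OCT: "All qualitative and quantitative parameters described above will be described overall at each visit". For CST, a paired t-test or Wilcoxon signed rank test "will be used to test the difference at each time point vs Baseline". For IRF, SRF, sub-RPE fluid, SHRM, ORT and ELM loss, "A McNemar test will be used to test the difference at each post-baseline visit vs baseline". On missing data: "An observed approach will be considered for all the analysis".

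SAP 6.3.2.1 (OCTA) follows the same scheme. In SAP 6.3.2.3 the paired test will "be used to test the BCVA ETDRS score difference at each time point vs Baseline"; LOCF is added for BCVA only as far as Week 16. SAP 6.5 plans no subgroup analyses, so none of these tables is split by regimen.

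The visit schedule is fixed elsewhere. Baseline and Weeks 4, 8, 12, 16 and 48 are mandatory (Protocol 6.7.2; SAP 3.3.1). Treatment visits run every 8 or 12 weeks counted from Week 8 (footnote 1 to Protocol Table 8-1), and no visits are planned between injections (Protocol 3). The regimen depends on the Investigator's disease activity assessment. SAP 1.1 acknowledges the consequence, "after Week 16 each patient will have different scheduled of visits based on treatment regimen", but uses it only as a reason to restrict LOCF.

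**The concern.** If the regimen depends on disease activity and the regimen decides which weeks a patient attends, then being present at an intermediate visit is itself a marker of response. An observed-case summary over all attenders at Week 20 is a summary of patients first judged suitable for q12w. The one at Week 24 is a summary of patients first put on q8w. The same schedule difference that led the SAP to give up LOCF after Week 16 applies equally to pooled observed-case results there.

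The secondary objectives concern the evolution of these parameters from Baseline to Week 48, so readers will go along the row of visits. They could then take a change in who attended for a change in the retina or in visual acuity.

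**Working it through.** **The plan's own figures.** The 56% and 122 used below come from SAP 3.5 and 3.1. The sample-size figures built on them reproduce: 1.96² × 0.56 × 0.44 / 0.06² = 262.9, rounded up to 263, and 2 × 1.96 × √(0.25/122) = 17.74%. Neither bears on this point.

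**Who attends when.** Counting from the Week 8 injection:
- q12w throughout: Weeks 20, 32, 44, then 48.
- q8w from Week 16: Weeks 24, 32, 40, 48.
- moved to q8w at Week 20: Weeks 28 and 36, then 44 if still on q8w.
- moved to q8w at Week 32: Weeks 40 and 48.
- returned to q12w at Week 32 after two visits without activity: Week 44.

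Nobody attends both Week 20 and Week 24. Weeks 28 and 36 contain only patients moved at Week 20.

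**Composition.** Inputs: 56% stay on q12w to Week 48 (SAP 3.5). More than 80% of those first judged suitable for q12w remain on it (Protocol 1.1), so the share first assigned q12w lies between 56% and 0.56/0.80 = 70%. Assumptions: activity at 40-100% of q8w visits, full attendance, no dropout.

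Worked case at one end of the range (70% first on q12w, 40% activity on q8w):
- Per-visit move from q12w: 1 - 0.80^(1/3) = 0.072.
- Week 20 share staying on q12w: 0.56/0.70 = 80%.
- Week 32 attendance: 1 - 0.70 × 0.072 = 95%; share 0.56/0.95 = 59%.
- Week 44 attendance: 0.70 × 0.928² + 0.70 × 0.072 × (1 - 0.6²) + 0.30 × 0.6² = 0.603 + 0.032 + 0.108 = 0.743; share 0.56/0.743 = 75%.

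Ranges over all cases:

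| Week | Attenders of 122 | Share staying on q12w | Weeks since last injection |
|---|---|---|---|
| 20 | 68-85 | 80-100% | 12 |
| 24 | 37-54 | 0% | 8 |
| 28, 36 | 0-6 | 0% | 8 |
| 32 | 116-122 | 56-59% | 12 or 8 |
| 40 | 29-54 | 0% | 8 |
| 44 | 68-90 | 75-100% | 12 or 8 |
| 48 | 122 | 56% | mixed (4 on unbroken q12w, 8 on unbroken q8w) |

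**Illustration.** The documents give no CST change by regimen, so the values are assumed: -150 µm in patients who stay on q12w, -90 µm in all others, constant over time. The all-patient mean is 0.56 × (-150) + 0.44 × (-90) = -123.6 µm. With share s at a visit, the size of the error is |s - 0.56| × 60:
- Week 20: 0.24 × 60 = 14.4 to 0.44 × 60 = 26.4 µm, overstating the reduction.
- Week 44: 0.19 × 60 = 11.4 to 26.4 µm, same direction.
- Weeks 24 and 40: 0.56 × 60 = 33.6 µm, understating it.
- Week 32: at most 0.03 × 60 = 1.8 µm.

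Between Weeks 20 and 24 the pooled mean would move by 48-60 µm although no patient changed. With a 30 µm gap every figure halves; with no gap all are zero; with a reversed gap the directions swap.

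**The case against.** The strongest defence is that paired t, Wilcoxon and McNemar tests set each patient against his or her own baseline, and the shift tables require both values. This stands. A reader might infer that the tests compare different patients and are invalid; they are valid for those who attended. What fails is generalising to everyone, or reading across visits.

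Other stronger readings also go beyond the documents:
- That every visit from Week 20 to Week 44 is affected. Both stable regimens attend Week 32, where only patients moved to q8w at Week 20 are absent.
- That Weeks 20 and 44 show only good responders, and Weeks 24 and 40 only poor responders on treatment. Week 20 includes patients who switch later, and Week 44 includes patients who have switched either way. Patients who stop treatment before Week 16 move to bimonthly visits (Protocol 9.1.1), which would fall at Weeks 24, 32 and 40 if counted every 8 weeks from Week 16.
- That a plotted mean curve will mislead. None is planned for these endpoints. The CST and BCVA spaghetti plots show individual courses, though by lesion type and not by regimen.
- That the results show attendance instead of a drug effect. They mix the two.

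Testing at every time point is also in Protocol 12.5.1, so the SAP is carrying out the protocol. It will report the number of patients entering each visit (6.1) and the first regimen chosen (6.4.1). That discloses changing denominators but does not remove the selection.

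**Conclusion.** The point holds for Weeks 20, 24, 28, 36, 40 and 44. At those visits the pooled summaries and tests of OCTA, SD-OCT and BCVA apply to patients selected through disease activity. They neither describe the study population nor join into one trajectory.

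That attendance differs by regimen follows from the documents' own rules. The attendance ranges also need the assumptions above, and the micrometre figures depend wholly on the assumed gap between regimens.

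A reader might infer that the Week 48 result or the primary analysis is compromised. The documents do not support that: the predictors are taken up to Week 16 and the outcome at Week 48, all at visits required of everyone. Time since injection does differ by regimen at Weeks 32 and 48, but that is not selection of who attends. Dropout and ungradable images are separate matters. This is a worthwhile, inexpensive correction to secondary outputs.

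**What to change.** In SAP 6.3.2.1 to 6.3.2.3, keep pooled summaries and tests for Weeks 4, 8, 12, 16 and 48, and give Week 32 as supportive with n shown. Present Weeks 20, 24, 28, 36, 40 and 44 descriptively by current regimen, with n and time since last injection, and state that pooled results at these visits are not interpreted as the population's course. Record the change in SAP 1.1, since it departs from the testing in Protocol 12.5.1.

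In the same edit, reconcile SAP 4.4.2, which still names LOCF for secondary endpoints, with SAP 1.1 and the endpoint sections, which restrict or drop it.

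The cost is SAP wording, revised table shells and fewer pooled p-values at intermediate visits. No new data are needed.
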